8.2 Participating Sites

Participating sites are responsible for performing the following tasks:

- Following the protocol as written, guidelines consistent with good clinical practice (GCP), and applicable Standard Operating Procedures (SOPs). Registering all patients

- with the coordinating center by submitting the eligibility checklist, supporting source documentation, and signed informed consent promptly
- Providing sufficient experienced clinical and administrative staff and adequate facilities and equipment to conduct a collaborative trial according to the protocol
- Maintaining regulatory binders on site and providing copies of all required documents to the coordinating center
- Collecting and submitting data according to the schedule specified by the protocol
- Responding to queries in a timely manner

8.3 Coordinating Center

The Coordinating Center is responsible for performing the following tasks:

- Ensuring that IRB approval has been obtained at each participating site prior to the first patient registration at that site, and maintaining copies of IRB approvals and required regulatory documents from each site.
- Managing patient registration
- Developing and maintaining Clinical Data Management documents and procedures
- EDC development, setup of study database, and subsequent design changes
- Participating in review of content of the EDC against the protocol requirements
- EDC system administration (user/site accounts setup, maintenance and revocation)
- Data review, cleaning, query management and resolution
- Establishing procedures for documentation, reporting and submitting of AEs and SAEs.
- Reviewing SAEs
- Training participating sites on EDC
- Collecting and compiling data from each participating site
- Data reviewing from all participating sites
- Facilitating monitoring visits by securing selected source documents and research records from participating sites for review, or by monitoring at participating sites.

9. ETHICAL AND REGULATORY REQUIREMENTS

9.1 Ethical Conduct of the Study

The study will be performed in accordance with ethical principles that have their origin in the Declaration of Helsinki and are consistent with ICH/Good Clinical Practice, and applicable regulatory requirements

9.2 Subject Data Protection

AstraZeneca will not provide individual genotype results to subjects, any insurance company, any employer, their family members, general physician or any other third party, unless required to do so by law.

Extra precautions are taken to preserve confidentiality and prevent genetic data being linked to the identity of the subject. In exceptional circumstances, however, certain individuals might see both the genetic data and the personal identifiers of a subject. For example, in the case of a medical emergency, an AstraZeneca Physician or an investigator might know a subject's

identity and also have access to his or her genetic data. Also, Regulatory authorities may require access to the relevant files, though the subject's medical information and the genetic files would remain physically separate.

9.3 Informed Consent

Before obtaining consent, members of the study team will review the rationale for the treatment program with the patient. The discussion will review the alternatives available (including hormonal therapy, chemotherapy, or supportive care as appropriate), the potential benefits of this program, the risks and the probability of their occurrence, and the procedures to minimize these risks. Should an AE occur, the provisions available to ensure medical intervention will also be reviewed. Why the risks are reasonable in relation to the anticipated benefits, incentives, or costs that will or may be incurred as a result of participating in the study, as well as the efforts to maintain confidentiality, will also be discussed with the patient.

Patients will be required to sign and date an informed consent form that meets the requirements of the Code of Federal Regulations (Federal Register Vol. 46, No. 17, January 27, 1981, part 50) and the IRB. The medical record will include a statement that written informed consent was obtained (and document the date that it was obtained) before the patient is enrolled in the study. The original signed document will become part of the patient's medical record, a copy will be forwarded to the lead site/sponsor pursuant to sponsor registration and a copy will be sent home with each patient.

The consent form will include the following:

- the nature and objectives, potential toxicities, and benefits of the intended study
- the length of therapy and likely follow-up required
- alternatives to the proposed therapy (including available standard and investigational therapies)
- the name of the investigator(s) responsible for the protocol
- the right of the patient to accept or refuse treatment and to withdraw from participation in this study

9.4 Changes to the Protocol and Informed Consent Form

Before starting the study, the protocol must be approved by each institution's IRB or Independent Ethics committee (IEC). Amendments to the protocol may be made only with consent of the lead site/sponsor and are pending until approval by IRB before instating.

9.5 Protection of Privacy

Patients will be informed of the extent to which their confidential health information generated from this study may be used for research purposes. After this discussion, they will be asked to sign a Notice of Privacy Practice research authorization/HIPAA form. The original signed documents will become part of the patient's medical records, and each patient will receive a copy of the signed documents. The use and disclosure of protected health information will be limited to the individuals described in the research authorization form. The research authorization form must be completed by the principal investigator and approved by the IRB.

9.6 Terminating or Modifying the Study

AE and laboratory data from this trial will be assessed by the lead site on an ongoing basis. SAEs will be reviewed as they are reported to the lead site, and the medical monitor will make an assessment regarding the safety of continuing or modifying the study. The futility evaluation after 17 patients as described. This assessment will be shared with the investigators either in writing or as part of a teleconference. Should the assessment of either the lead site/sponsor or the principal investigator be that the study should be terminated, the study will be closed to further accrual. Patients who are receiving intervention will be assessed individually by the investigator to see if it is in the patients' best interest to continue, which might be the case for a patient that is responding to the intervention. Follow-up safety assessments will be performed for all patients who are terminated from the study prematurely.

10. STATISTICAL METHODS AND SAMPLE SIZE DETERMINATION

10.1 Study Endpoints

10.1.1 Analysis of the primary endpoint

The primary endpoint of the study is the response rate of the DRPro cohort. Response is defined as achieving a complete response (CR) or partial response (PR) by either radiographic response according to RECIST v 1.1 or PSA response. The count of responses and corresponding response rate with the 95% binomial confidence interval will be reported in the DRPro patients.

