Patients with progressive, metastatic, castration-resistant prostate cancer who received a) at least one line of systemic therapy for mCRPC or b) failed ongoing second generation anti-hormonal therapy (e.g. abiraterone) in the hormone-sensitive or non-metastatic castration resistant phases of disease. They must remain on continuous LHRH agonist/antagonist, unless they have undergone orchietomy.

Duration of treatment

Patients must have washed out of any prior systemic therapy for either 3 weeks or 5 half-lives (whichever is longest), excluding prednisone, LHRH agonist/antagonists, bisphosphonate or RANKL inhibitor. The median duration of study per patient is estimated to be approximately 12 months.

Investigational product, dosage and mode of administration

Olaparib, 300 mg by mouth, twice a day, days 1-28 of a 28-day cycle.
AZD6738, 160 mg by mouth, daily, days 1-7 of a 28-day cycle.

Statistical methods

For the DRPro population (characterized through study sequencing or previously completed), using an Optimal Simon 2-stage design, this cohort will be 35 total patients with an interim for futility after 17 DRPro patients have been accrued. If 2 or more responses are seen in the first stage, then the second stage will open and accrue 18 more DRPro patients. If 5 or more patient responses are seen out of the 35 DRPro patients, then the combination treatment will be deemed interesting for further study in a DRPro population. The null response rate from the

TOPARP-A study is 6%. The current design will detect at 80% power, a response rate of 20% or greater with 5% one-sided type I error.

For the DRDef population (characterized through study sequencing or previously completed), using a Mini-Max Simon 2-stage design. A set of 12 DRDef will be treated and if 6 or more responses are seen, this would support consideration to expand (with amendment or new protocol) with another 13 patients or a completely separate trial.

Principal analyses will report the response rate (CR/PR) per radiographic response according to RECIST v1.1 or PSA ($\geq 50\%$ decline) in DRPro and DRDef patients. The cohorts will be separated for all efficacy analyses.

TABLE OF CONTENTS		PAGE
	TITLE PAGE	1
	TABLE OF CONTENTS	6
	LIST OF ABBREVIATIONS AND DEFINITION OF TERMS	11
1.	INTRODUCTION.....	14
1.1	Background.....	14
	1.1.1 Pre-clinical experience.....	15
	1.1.2 Toxicology and safety pharmacology summary	15
	1.1.3 Clinical experience.....	16
1.2	Research Hypothesis	16

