10.1.2 Analysis of the secondary endpoints

- The response rate and 95% binomial confidence interval will be reported for DRDef patients.

The following endpoints will be reported for DRDef and DRPro patients separately

- Objective progression-free survival (combined radiographic and clinical progression-free survival) will be reported using Kaplan-Meier methods. This is measured from the date of treatment arm assignment until the specified tumor progression (assigned at the earliest observed time). Patients whose disease has not progressed at follow-up will be censored at the date when the last tumor assessment determined a lack of progression.
- Objective radiographic disease response rate is determined by the proportion of patients with measurable disease that have a response (CR+PR) according to RECIST v1.1. The proportion of responders will be reported with the corresponding 95% binomial confidence interval.
- PSA progression-free survival (PSA-PFS) will be reported as the composite of survival and duration of PSA control as defined by after a start of therapy from baseline to time of first PSA increase $\geq 25\%$ and ≥ 2 ng/mL above the nadir and confirmed by a second value at or beyond 4 weeks later. Kaplan-Meier methods will be used to report PSA-PFS.

- PSA response rate (≤ 0.2 ng/ml, 50% decline, 90% decline) proportions will be reported with corresponding 95% binomial confidence intervals. A waterfall plot of the best PSA response decline will be reported.
- Evaluate the qualitative and quantitative AE summaries will be reported by DNA repair status and organized by body system, frequency of occurrence, intensity (e.g. severity grade) and causality or attribution. Counts and proportions will be included. Treatment exposure will be summarized for all patients, including dose administration, number of cycles, dose modifications or delays and duration of therapy. Categorical variables will be reported using counts and frequencies. Continuous variables will be summarized using means or medians with the appropriate measure of variability.
- Duration of combined radiographic and PSA response will be reported using Kaplan-Meier methods.

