10.3.5 Statistical procedures

Summary statistics include the number of observations, mean, standard deviation, median, minimum, and maximum values. As this is not a comparative trial, p-values will be used sparingly.

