10.3.6 Sample size calculation

The statistical design for DRPro will be an Optimal Simon 2-stage Phase II. Based on the TOPARP-A study the null response rate for DRPro is 6% and a response rate of 6% or less would not be interesting. Accrual of 35 DRPro patients will provide 80% power to detect a response rate of 20% or greater with 5% type I error. Stage 1 will accrue 17 DRPro patients. If 1 or less DRPro patients have a preliminary response (CR/PR using radiographic by RECIST v.1.1 or PSA decline $\geq 50\%$) then the DRPro cohort will stop. If 2 or more responses occur, then the 2nd stage will begin and another 18 DRPro patients will be accrued. If 5 or more patient responses are seen out of the 35 DRPro patients, then the combination treatment will be deemed interesting for further study in the DRPro population.

The statistical design for the DRDef is a Mini-Max Simon 2-stage Phase II. Based on a response rate of 45% within the first 12 weeks in TOPARP-A, a response rate of under 45% would not be interesting. Stage 1 of this design requires 12 DRDef patients and if 5 or less patients have a preliminary response (CR/PR using radiographic by RECIST v.1.1. or PSA decline $\geq 50\%$), then the DRDef cohort would not be of interest. If 6 or more patients do respond, this would support consideration to expand (with amendment or new protocol) with another 13 patients (to a total of 25 patients) or a completely separate trial. Accrual of 25 patients would provide 80% power to detect a response rate of 70% or greater with 5% type I error. If 16 or more patient responses were seen in a 25 total DRDef patient cohort, then the combination treatment would be deemed interesting for further study DRDef. Different RR are used for DRDef and DRPro as different expected baseline RR.

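### Does the unnamed 95% binomial interval in section 10.1.1 undercut the 5-of-35 success rule for the DRPro cohort?

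*Combined protocol and SAP*

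**What the plan says.** The primary analysis in section 10.1.1 is one sentence: "The count of responses and corresponding response rate with the 95% binomial confidence interval will be reported in the DRPro patients". Section 10.1.2 uses the same form for the other cohort: "The response rate and 95% binomial confidence interval will be reported for DRDef patients". Neither names an interval method.

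The decision is set elsewhere. In section 10.3.6, "The statistical design for DRPro will be an Optimal Simon 2-stage Phase II", with a 6% null taken from TOPARP-A. The cohort stops if 1 or fewer of the first 17 patients respond. Otherwise 18 more are accrued, and "If 5 or more patient responses are seen out of the 35 DRPro patients, then the combination treatment will be deemed interesting". The synopsis gives the error rates and the sidedness: "The current design will detect at 80% power, a response rate of 20% or greater with 5% one-sided type I error". On tests in general, section 10.3.5 adds: "As this is not a comparative trial, p-values will be used sparingly".

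No section says that the interval will be compared with 6% or will bear on the decision.

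**The concern.** The term binomial covers a family of intervals, and the trial has an interim futility look that a single-stage interval ignores. With few p-values planned, readers may set the reported interval against the 6% null. At the lowest successful result, 5/35, most common methods give an interval that contains 6%, although the trial would be declared positive. One method, Wilson, excludes 6%. In principle the method could be picked after the data are seen to suit the message. What is at stake is how a borderline success is reported. The go decision, its type I error and its power are not in question.

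**Working it through.** **Inputs** (section 10.3.6; sidedness from the synopsis): first stage 17 patients, stop at 1 or fewer responses; second stage 18 more; success at 5 or more of 35; null rate 6%; target rate 20%; one-sided type I error 5%; power 80%.

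**1. The plan's own figures.** With X1 ~ Bin(17, p) and X2 ~ Bin(18, p), the chance of success is P(X1 ≥ 2 and X1 + X2 ≥ 5).
- At p = 0.06: 0.0474, under the 5% cap.
- At p = 0.20: 0.802, so 80% power holds.

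A search over designs with up to 41 patients returns the same optimal design.

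**2. Intervals at 5/35 (14.3%).** The exact 95% limits are beta quantiles: lower Beta(0.025; 5, 31) = 4.8%, upper Beta(0.975; 6, 30) = 30.3%. The Wald lower limit is 0.1429 − 1.96 × √(0.1429 × 0.8571 / 35) = 0.027. All six methods compared:

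| 95% method | Lower limit at 5/35 | Contains 6%? |
|---|---|---|
| Wald | 2.7% | yes |
| Clopper-Pearson | 4.8% | yes |
| Mid-P | 5.4% | yes |
| Jeffreys | 5.7% | yes |
| Agresti-Coull | 5.8% | yes |
| Wilson | 6.3% | no |

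**3. Why rule and interval differ.** An exact two-sided 95% interval excludes 6% from below only if the one-sided p-value against 6% is under 0.025. The count rule needs only p ≤ 0.05 under the two-stage design.
- At 5/35, p = 0.0474 two-stage and 0.0563 single-stage. The first meets 0.05; neither meets 0.025.
- At 6/35, the single-stage p = 0.0168 is under 0.025. The exact lower limit is 6.6%, so interval and rule agree.

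**4. What a two-stage adjustment would do.** Inverting the two-stage tail probability at 5/35 gives:
- 95%: 5.0% to 31.8%, still containing 6%.
- 90%: 6.1% to 29.0%, excluding 6%. At 4/35 the lower limit is 4.5%.

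The single-stage exact 90% interval is 5.8% to 27.7% and also contains 6%. Agreement at the boundary therefore needs both the 90% level and the two-stage method.

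**5. How often it arises.** P(exactly 5/35) is 3.2% at a true 6%, 11.2% at 10%, 15.3% at 15% and 10.5% at 20%. At 20% that is 0.105 / 0.802 = 13% of successes. With Wald, 6/35 also conflicts (lower limit 4.7%), and 5 or 6 of 35 together have probability 24.9% at a true 20%, or 0.249 / 0.802 = 31% of successes.

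**6. Is the planned interval valid?** Under the two-stage design, coverage at true rates of 6%, 10% and 20% is:
- ordinary exact 95% interval: 98.5%, 98.0%, 96.0%;
- two-stage 95% interval: 98.5%, 98.0%, 96.3%.

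**The case for a change.** The strongest case for a change is that it is cheap and the outcome is not remote. A sentence naming the method, and another stating that the interval is descriptive, would close off a choice after the data are seen. It would serve the DRDef, radiographic and PSA response rates as well. At a true rate of 10%, 5/35 makes up 0.112 / 0.234 = 48% of successes. A reader who ran an ordinary exact test on a declared success at 5/35 would get p = 0.056. A two-stage p-value and 90% interval would show that the decision and the data agree.

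Some of this stands. The method is not named, and naming it would be good reporting practice. The rest is weaker.
- The room for choice is narrow: five of the six methods read the same way at 5/35, and nothing in the documents points to Wald, on which the larger figures depend.
- The count rule is already stated in both the synopsis and section 10.3.6, so the interval cannot overturn it.
- The two-stage 90% interval excludes 6% in every successful trial by construction, including the 4.7% of trials that succeed when the true rate is 6%. Against 6% it restates the count rule, at a level the plan never proposed.
- A bias-adjusted estimate (UMVUE, 16.4% at 5/35 against the raw 14.3%) brings no consistent gain. Its root mean squared error is larger at a true 6% (0.055 against 0.044) and slightly smaller at 20% (0.076 against 0.080).

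**Conclusion.** No change follows. The omission is real, but it is missing reporting detail that a competent analyst supplies without harm. Followed as written, the plan gives a decision with type I error 0.0474 and power 0.802. With the ordinary exact method, it gives an interval that covers at least 96% at the three true rates checked. The apparent conflict at 5/35 is the expected difference between a one-sided 5% test and a two-sided 95% interval. At the planned 95% level a two-stage adjustment moves the lower limit by about 0.2 percentage points (4.8% to 5.0%), leaves 6% inside and barely alters coverage.

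This rests on three assumptions: the analysed numbers are the planned 17 and 35; the analyst uses the exact interval or one close to it; and the interval is read as a description of precision, with the count deciding, as the synopsis and section 10.3.6 provide. If Wald were used, the disagreement would extend to 6/35, but the decision would still not be affected.

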10.1.2 Analysis of the secondary endpoints

- The response rate and 95% binomial confidence interval will be reported for DRDef patients.

The following endpoints will be reported for DRDef and DRPro patients separately

- Objective progression-free survival (combined radiographic and clinical progression-free survival) will be reported using Kaplan-Meier methods. This is measured from the date of treatment arm assignment until the specified tumor progression (assigned at the earliest observed time). Patients whose disease has not progressed at follow-up will be censored at the date when the last tumor assessment determined a lack of progression.
- Objective radiographic disease response rate is determined by the proportion of patients with measurable disease that have a response (CR+PR) according to RECIST v1.1. The proportion of responders will be reported with the corresponding 95% binomial confidence interval.
- PSA progression-free survival (PSA-PFS) will be reported as the composite of survival and duration of PSA control as defined by after a start of therapy from baseline to time of first PSA increase $\geq 25\%$ and ≥ 2 ng/mL above the nadir and confirmed by a second value at or beyond 4 weeks later. Kaplan-Meier methods will be used to report PSA-PFS.

- PSA response rate (≤ 0.2 ng/ml, 50% decline, 90% decline) proportions will be reported with corresponding 95% binomial confidence intervals. A waterfall plot of the best PSA response decline will be reported.
- Evaluate the qualitative and quantitative AE summaries will be reported by DNA repair status and organized by body system, frequency of occurrence, intensity (e.g. severity grade) and causality or attribution. Counts and proportions will be included. Treatment exposure will be summarized for all patients, including dose administration, number of cycles, dose modifications or delays and duration of therapy. Categorical variables will be reported using counts and frequencies. Continuous variables will be summarized using means or medians with the appropriate measure of variability.
- Duration of combined radiographic and PSA response will be reported using Kaplan-Meier methods.

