2.2 Secondary Objectives

Secondary Objective:	Outcome Measure:
To determine the response rate of the combination of olaparib and AZD6738 in mCRPC patients who are DNA repair deficient (mono- or biallelic somatic ATM loss OR biallelic somatic loss of BRCA1 or BRCA2 OR known mono or biallelic germline loss of ATM, BRCA1, or BRCA2).	The rate of response (CR/PR) per radiographic response according to RECIST v1.1 or PSA ($\geq 50\%$ decline) in DRDef patients.
All of the below secondary objectives will be calculated for the DRPro, DRDef patients separately.	
Objective progression-free survival (combined radiographic and clinical progression-free survival)	The objective progression-free survival is the duration of time from start of treatment to date of progression (based only on radiographic progression or clinical decline/death).
Objective radiographic disease response rate	The rate of achieving a radiographic response according to RECIST v1.1.
PSA progression-free survival	Composite of survival and duration of PSA control as defined by time from start of therapy to first PSA increase $\geq 25\%$ and ≥ 2 ng/ml above the nadir and confirmed by a second value at or beyond 4 weeks later.
PSA response rate for ≤ 0.2 ng/ml, 50% decline, 90% decline from entry PSA and confirmed 4 weeks later	The rate of achieving the aforementioned PSA value or percent decline compared to PSA at entry.
Duration of combined radiographic and PSA response	Time from first documented response (RECIST v1.1 CR/PR or PSA decline $\geq 50\%$) until death, recurrent or progressive disease (based on RECIST v1.1) or first PSA increase $\geq 25\%$ and ≥ 2 ng/ml above the PSA nadir.

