5.6 Discontinuation of Investigational Product

Subjects may be discontinued from protocol treatment in the following situations:

- Subject decision. The subject is at any time free to discontinue treatment, without prejudice to further treatment
- Adverse Event
- Severe non-compliance with the study protocol
- Bone marrow findings consistent with myelodysplastic syndrome (MDS)/acute myeloid leukemia (AML)
- Disease Progression (as defined by Section 7.6.7). In the absence of other indicators of disease progression, therapy should not be discontinued based on PSA rise alone.

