5.6.2 Duration of follow-up

Patients will be followed for 30 days after removal from treatment or until death, whichever occurs first. Patients removed from treatment for unacceptable adverse events will be followed until resolution or stabilization of the adverse event.

All patients should be followed for MDS/AML and new primary malignancy assessment for up to 5 years after the patient completes the study per Section 7.7.1.

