7.6.1 PSA

Perform PSA testing at a minimum of 4-weeks intervals with the threshold PSA level at 1.0 ng/mL. To report PSA-based outcomes, PCWG3 recommends that the percent of change in PSA from baseline to 12 weeks (or earlier for those who discontinue therapy) and the maximum decline in PSA that occurs at any point after treatment be reported for each patient. PSA rise alone is insufficient to define progression within the study (see Section 7.6.7).

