7.6.7 Progression/response criteria

Non-lethal disease progression (necessitating discontinuation from trial) is either clinical progression (see Section 7.6.7.5) or radiographic progression based on RECIST (see Section 7.6.7.1, 7.6.7.2) or PCWG3 bone scan criteria (see Section 7.6.7.4). These are combined and

shown in graphical format in Section 7.6.8. Confirmatory bone scan ≥ 4 weeks after first bone scan progression per PCWG3 is required and must show ≥ 2 new lesions.

PSA progression alone is NOT sufficient for removal from study.

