7.6.7.4 Outcomes based on post-therapy PSA changes

These definitions are intended to characterize the PSA changes on study for the purpose of reporting of results. PSA progression is NOT criteria to remove from study.

Complete Response (CR): Undetectable PSA (\leq 0.2 ng/ml) that is confirmed by another PSA level at no less than 4 weeks interval.

Partial Response (PR): Decrease in PSA value by \geq 50% that is confirmed by another PSA level at no less than 4 weeks interval.

Stabilization (SD): Patients who do not meet the criteria for PR or PD for at least 90 days on study (2 cycles of treatment) will be considered stable

Progression (PD): 25% increase over baseline or nadir whichever is lower and an increase in the absolute value of PSA level by 2 ng/ml that is confirmed by another PSA level at no less than 4 weeks interval.

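### A PSA rise first seen at the final 30-day draw can never be confirmed, so PSA-PFS as defined censors it at the moment of progression and the Kaplan-Meier curve is pushed upward

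*Combined protocol and SAP*

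**What the plan says.** - **Event.** Section 2.2 defines PSA-PFS as "Composite of survival and duration of PSA control as defined by time from start of therapy to first PSA increase" of at least 25% and at least 2 ng/ml above the nadir. Section 10.1.2 requires the rise to be "confirmed by a second value at or beyond 4 weeks later. Kaplan-Meier methods will be used to report PSA-PFS". Section 7.6.7.4 defines PSA progression with the same condition: "that is confirmed by another PSA level at no less than 4 weeks interval".
- **PSA schedule.** Section 7.6.1: "Perform PSA testing at a minimum of 4-weeks intervals". The Section 5 calendar places PSA on Day 1 of each 28-day cycle and at the 30 (±3) day visit. Long-term follow-up covers only MDS/AML and new malignancy. Section 5.6.2: "Patients will be followed for 30 days after removal from treatment or until death, whichever occurs first".
- **End of treatment.** Section 5.6 says that, without other signs of progression, "therapy should not be discontinued based on PSA rise alone". Section 7.6.7: "Non-lethal disease progression (necessitating discontinuation from trial) is either clinical progression" or radiographic progression.
- **Censoring.** Section 10.1.2 gives a censoring rule for objective PFS and none for PSA-PFS.

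**The concern.** Confirmation needs a later draw, but the schedule ends at a fixed visit whose timing is set by something other than PSA. For a rise that first appears at that visit, the plan asks for a value it does not collect. The patient then enters the Kaplan-Meier estimate as a non-event on the date his PSA met the rise criterion. If removal and PSA progression tend to come together, as they would when men leave for radiographic or clinical progression, this censoring is informative and PSA control looks longer than it was.

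The plan also treats the same observation in two ways. Duration of response (2.2, 7.6.9) ends at the first qualifying PSA increase with no confirmation. A last-draw rise can therefore end a responder's duration of response without being a PSA-PFS event.

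PSA-PFS is a named secondary endpoint in both cohorts, and two analysts could report different curves from the same data.

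**Working it through.** The documents state no PSA-PFS median, rate or event count, so there is no figure to reproduce.

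**1. Which rises cannot be confirmed**

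If a rise is first seen on the last Day 1 draw and the last dose is *d* days later, the gap to the final draw is *d* + 27 to *d* + 33 days.
- *d* = 0: 27-33 days. Confirmation fails only if the visit falls on day 27.
- *d* ≥ 1: at least 28 days, so always confirmable.
- Rise first seen at the final draw: no later scheduled value, so never confirmable.

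From cycle 3 the window is -5 to +3 days, so adjacent Day 1 draws can be 28 - 8 = 20 to 28 + 8 = 36 days apart. A gap under 28 days only delays confirmation while another draw follows. The problem is therefore essentially the final draw.

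**2. What Kaplan-Meier does with such a rise**

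At each time the curve is multiplied by (1 - events / number at risk). A counted rise contributes 1 to the events. An unconfirmed rise contributes 0 and the patient leaves the risk set, so the curve stays higher.

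**3. Size**

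Assumptions, not from the documents: exponential times to PSA progression and to removal, joined by a Gaussian copula with correlation 0 or 0.5; draws every 28 days on treatment and one 30 days after removal; every rise persistent; no deaths; 200,000 simulated patients per row. The only duration in the documents is the synopsis estimate of about 12 months on study, which is not time on treatment.

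The grid truth column is the 6-month rate if 28-day draws had continued regardless of removal. Differences are from unrounded values.

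| Median months, PSA / removal | Corr. | No rise before PSA stops | Rise only at last draw | 6-month rate, as written | 6-month rate, last rise counted | Difference (points) | Grid truth | Median months, as written / counted |
|---|---|---|---|---|---|---|---|---|
| 3 / 5 | 0 | 30.0% | 11.6% | 33.4% | 26.3% | 7.1 | 27.7% | 3.7 / 3.7 |
| 3 / 5 | 0.5 | 21.9% | 17.3% | 39.7% | 30.3% | 9.4 | 27.9% | 4.6 / 3.7 |
| 4 / 4 | 0 | 42.4% | 11.8% | 45.3% | 36.3% | 9.0 | 38.4% | 5.5 / 4.6 |
| 4 / 4 | 0.5 | 38.0% | 18.5% | 55.0% | 42.1% | 12.9 | 38.5% | 6.4 / 4.6 |
| 4 / 6 | 0 | 33.9% | 9.5% | 43.3% | 37.4% | 5.9 | 38.7% | 4.6 / 4.6 |
| 4 / 6 | 0.5 | 26.7% | 14.6% | 49.7% | 41.1% | 8.6 | 38.4% | 5.5 / 4.6 |
| 5 / 5 | 0 | 43.6% | 9.6% | 51.5% | 44.7% | 6.8 | 46.5% | 6.4 / 5.5 |
| 5 / 5 | 0.5 | 40.1% | 15.3% | 60.7% | 50.3% | 10.4 | 46.6% | 8.3 / 6.2 |
| 4 / 12 | 0 | 21.0% | 5.9% | 40.7% | 37.8% | 2.9 | 38.4% | 4.6 / 4.6 |
| 4 / 12 | 0.5 | 12.3% | 8.6% | 44.3% | 40.0% | 4.4 | 38.6% | 5.5 / 4.6 |

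- Affected share: 5.9% to 18.5%. That is about 2 to 7 of 35 DRPro patients and about 1 to 2 of 12 DRDef patients.
- The as-written rate lies about 2 to 17 points above the grid truth. Counting last-draw rises brings it within 4 points either way.
- The median is unchanged in 3 rows, moves by one 28-day visit in 5, and by about two visits in 2.
- For scale, the standard error of a 50% rate at n = 35 is √(0.5 × 0.5 / 35) = 8.5 points.

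**4. Cross-check**

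A separate simulation used the protocol's visit windows, PSA medians of 2, 3 or 5 months, correlation 0 or 0.6, and 70% or 100% attendance at the 30-day visit. The unconfirmable share was 5-9% at a 12-month treatment median, 9-18% at 6 months and 12-29% at 3 months. Shorter treatment makes the problem larger.

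**The case against.** **No censoring rule is written for PSA-PFS, so the bias is assumed.** The missing rule is a fact, but it does not remove the problem. The event definition excludes an unconfirmed rise, and a patient without an event is censored. Avoiding this means departing from the definition, which is why a rule has to be written.

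**The schedule mostly works.** This stands. Treatment and 4-weekly PSA continue through a PSA rise, so confirmation is normally collected, and a rise at the last on-treatment draw is usually confirmable at the 30-day visit.

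**Death is already covered.** This largely stands. The endpoint is called a "composite of survival and duration of PSA control", so death is meant to be an event. Only the time clause, which runs to the PSA increase alone, is loose. A reader might infer that every man who leaves, including those who die, is a non-event. The documents do not support that.

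**Many patients cannot be scored.** A reader might add the columns, for example 26.7% + 14.6% = 41.3% in the 4 / 6, correlation 0.5 row. That sum mixes two things. Men with no rise before PSA stops (12-44% across the rows) are censored because collection ends, not because of confirmation, and counting last-draw rises does not change them.

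**Confirmation guards against transient rises.** Fair. The model makes every rise real, so it overstates what confirmation would have kept. This is a reason to show both curves.

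**The stakes are modest.** This stands. The endpoint has no threshold or test, and most of the shifts are near or below one standard error at n = 35. The 25% in Section 10.3.4 is a toxicity stopping threshold, not an expected removal rate, and adds nothing on size.

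**Conclusion.** The point holds in a limited form. The confirmation rule and the end of PSA collection together make a last-draw rise impossible to score, and the resulting censoring favours the treatment.

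Under the assumed timings, about 6-19% of patients are affected and 6-month PSA-PFS is raised by about 3-13 points. Both are smallest with a 12-month median to removal (about 6-9% of patients, 3-4 points), and the affected share is larger if treatment is much shorter than in these scenarios. The direction follows from the definitions. The size rests on timings the documents do not give, and on leaving out deaths and transient rises.

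The documents do not show that most PSA events are lost, and the primary response-rate decision is not touched.

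**What to change.** In the synopsis, 2.2 and 10.1.2, for PSA-PFS only:

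1. Count a qualifying rise on the last available PSA, with no later value, as an event on that date. Report the confirmed-only curve beside it.
2. Word the time clause so that death before PSA progression is an event, and say how long deaths are collected. Section 5.6.2 stops at 30 days, while 7.7.10.2 refers to follow-up for overall survival.
3. Censor all other patients at their last PSA.
4. Add one supportive curve that counts removal for radiographic or clinical progression as an event, because censoring these men in the main curve may itself be informative.

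Section 7.6.7.4 can keep confirmation for its PSA categories, with a pointer to the PSA-PFS exception so that the sections do not conflict.

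The PSA rules need no new visits. The cost is wording and two extra curves per cohort. A few last-draw rises might not have been confirmed, so the reported figure becomes slightly less favourable.
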